The primary analysis will evaluate the efficacy of galcanezumab compared with placebo on the overall mean change from baseline in the number of monthly migraine headache days during the 3-month double-blind treatment phase. Migraine headache day is defined to include both migraine and probable migraine days. The primary analysis will be performed using a restricted maximum likelihood-based mixed model repeated measures technique.

2. Schedule of Activities

Table CGAW.1. Schedule of Activities

Study Period	SP I Screening	SP II Prospective Baseline	SP III Double-Blind Treatment			SP IV Open-Label Treatment				Notes	
(Target) Interval (days) since previous visit			30-45	30	30	30	30	30	30		
Allowable range (days) between visits	3-30	30-40 ^a								ET	
Interval allowance (days)				±2	±2	±2	±2	±2	±2		
Visit	1	2	3	4	5	6	7	8	9		
Month			0	1	2	3	4	5	6		
Assessments and Procedu	res										
Informed consent	X										
Inclusion/exclusion	X	X	X								
Demographics	X										
Physical examination	X										
Neurological examination	X								X	X	
Height	X										
Weight	X		X			X			X	X	
Medical history	X										
Substance use	X										Substances: alcohol, caffeine, nicotine, tobacco
ECG	X		X			X	_		X	X	Predose and prior to blood draws. See Section 9.4.1.

Schedule of Activities

Study Period	SP I Screening	SP II Prospective Baseline	ective SP III Open-Label				Open-Label		ET	Notes	
Visit	1	2	3	4	5	6	7	8	9		
Month			0	1	2	3	4	5	6		
Vital signs	X		X	X	X	X	X	X	X	X	Includes body temperature, sitting blood pressure, and pulse. Predose and prior to blood draws. See Section 9.4.2.
Adverse events	X	X	X	X	X	X	X	X	X	X	
Concomitant medications	X	X	X	X	X	X	X	X	X	X	
ePRO and headache medication log training		X									
ePRO daily patient entries		X	X	X	X	X	X	X	X	X	
Headache medication log		X	X	X	X	X	X	X	X	X	
Patient training video			X								
Clinical Laboratory Tests	and Samplin	g Schedule									
Hematology	X		X			X			X	X	See Appendix 2.
Clinical chemistry ^b	X		X			X			X	X	Fasting is not required. See Appendix 2.
HbA1c			X			X			X	X	Fasting is not required.
Urinalysis	X		X			X			X	X	See Appendix 2. In the event of a positive urine leukocyte esterase result, a repeat urine sample will be collected and shipped to the central laboratory.

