The daily data will reflect whether the patients meet the migraine / probable migraine criteria; those data will be aggregated, and the number of migraine headache days will be provided for each of the 30-day periods. In calculating the number of migraine headache days for each period, if the period is not equal to 30 days, the number of migraine headache days will be adjusted by multiplying the number of migraine headache days by (30/x) where 'x' is the total number of non-missing diary days in the period.

This approach to missing ePRO diary data assumes that the rate of migraine headache per day is the same for days with missing and non-missing ePRO diary days. The same approach will also be applied to secondary and exploratory efficacy measures that are derived from ePRO data.

Additionally, if the compliance rate for a monthly interval is \leq 50%, then all endpoints to be derived from the ePRO diary data for that 1-month period will be considered missing. The compliance rate will be calculated as described in Section 5.5.7.

Other Secondary and Exploratory Efficacy Measures

The same approach for adjusting the number of days within each period to a 30-day period and the same approach to imputing monthly data based on compliance as for the primary measure will be applied to all efficacy measures that are derived from ePRO diary data and need normalization to a 30-day period, including:

- Number of ICHD migraine headache days is calculated as the number of calendar days in a 30-day period on which a migraine occurs. Probable migraine is excluded.
- **Number of headache days** is calculated as the number of calendar days in a 30-day period on which a headache occurs.
- **Number of migraine headache hours** is calculated as the total number of headache hours in a 30-day period on days when a migraine or probable migraine occurs.
- **Number of headache hours** is calculated as the total number of headache hours in a 30-day period on which a headache occurred.
- Number of days with acute headache medication use is calculated as the number of calendar days in a 30-day period on which abortive medication is used.

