5.5.1.2. Handling of Dropouts or Missing Data

Two statistical approaches to handling missing data will be used as appropriate: repeated measures analyses and ANCOVA/ANOVA model using change from baseline to LOCF endpoint.

For the repeated measures analyses, the model parameters are simultaneously estimated using restricted likelihood estimation incorporating all of the observed data. Estimates have been shown to be unbiased when data are missing at random.

Please refer to Section 5.4.1 for approach to handling missing diary data for derivation of migraine headache days and other efficacy measures (with the exception of migraine attacks) derived from ePRO data per 30-day period.

Approaches to handling missing diary data for the derivation of migraine attack

For the derivation of the number of monthly migraine attacks, the LOCF method will be used to impute the missing ePRO diary days. If the patient was migraine headache-free on the day before the missing ePRO diary day, this would be carried forward as no migraine headache day until the actual next non-missing diary day. On the other hand, if the day before the missing ePRO diary day is a migraine headache day, then it would be carried forward as migraine headache day until the next non-missing diary day. The imputation will be carried out for all the missing diary days between the first non-missing to the last day.

If the diary compliance rate for a monthly interval is \leq 50%, the number of monthly migraine attacks during that month will be considered missing. Please refer to Section 5.5.7 for diary compliance rate calculation.

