5.5.7. Electronic Patient-Reported Outcomes Diary Compliance

Electronic patient-reported outcomes diary compliance at each 1-month period (including baseline, Month 1, Month 2, ... to Month 6) as well as for SP III overall (Month 1 through Month 3) will be calculated. Diary compliance at each 1-month period is calculated as:

 $\frac{\text{Actual number of diary days in the period}}{\text{Expected number of diary days in the period}}*100$

Expected number of ePRO diary days is calculated as date of injection at the end of the interval minus date of injection at the beginning of the interval +1.

For a patient who discontinues early in the double-blind (SP III) or open-label treatment phase (SP IV), compliance rate for the last month of that patient will be calculated with a denominator of 30 days (or the actual number of days in the interval if it is greater than 30).

Treatment comparisons for ePRO diary compliance for SP III will be performed using an ANOVA with treatment, baseline migraine frequency category, and pooled country in the model. ePRO diary compliance for SP IV will be summarized.

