To assess the robustness of the MMRM results to deviations from normality assumption, a sensitivity analysis for raw number of migraine headache days (total number of migraine headache days for each interval without normalization to 30-day period) will be conducted with a repeated measures negative binomial regression model fitted with SAS PROC GLIMMIX. The model will include treatment, pooled country, month, and treatment-by-month interaction, as well as the continuous fixed covariates of baseline number of monthly migraine headache days and baseline-by-month interaction, log (number of compliant days within each month/30) as the offset in the model. In case of non-convergence, pooled country and/or baseline-by-month interaction may be excluded from the model. Directional consistency of treatment effects from this model and the primary analysis MMRM model as specified in Section 5.5.10.1 will be examined.

In addition, as another form of sensitivity analysis, residuals from the primary analysis MMRM model will be examined and outliers identified. Consistency of results before and after removing patients with outlier residuals will be examined.

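### SAP 5.4.1 triggers the 30/x diary adjustment on period length although x counts completed diary days: a wording error that, read literally, leaves a 30-day period with missing entries unadjusted

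*SAP*

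**What the plan says.** SAP 5.4.1 (Primary Measure) builds each monthly count from daily diary data and then states the rule: "if the period is not equal to 30 days, the number of migraine headache days will be adjusted by multiplying the number of" such days by 30/x. It defines x as the diary days in the period that are not missing. The sentence after that describes the rule as the way missing diary data are handled, and says that it "assumes that the rate of migraine headache per day is the same for days with missing and non-missing ePRO diary days". A month with diary compliance of 50% or less is set to missing.

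The scope is wide. For the other normalized diary measures, 5.4.1 carries over "The same approach for adjusting the number of days within each period to a 30-day period". The X% responder indicators are derived from the same monthly counts.

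Two other places bear on intent:

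- SAP 5.5.1.2 sends the reader back to 5.4.1 for the approach to "handling missing diary data for derivation of migraine headache days and other efficacy measures (with the exception of migraine attacks"). Attacks have their own imputation rule.
- The negative binomial sensitivity model in SAP 5.5.10.2 takes raw counts and uses "log (number of compliant days within each month/30) as the offset in the model", with no condition on period length.

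**The concern.** The condition and the divisor are different quantities. Period length says how far apart the boundaries are; x says how many diary days between them were completed. They agree only when nothing is missing. A period counted as 30 days with 24 entries fails the condition, so the sentence as written leaves its count alone, and the six days without an entry contribute zero migraine days. That contradicts the equal-rate assumption stated immediately afterwards.

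This is the operative derivation for the primary endpoint and for the 50% and 75% response rates, which are key secondary endpoints in the gated sequence. If the clause were programmed word for word, the same diary would give different values depending only on whether its interval counts as 30 days.

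**Working it through.** The documents state no figure that depends on this clause, so there is none to reproduce. The check compares the two readings. The recorded counts below are illustrative assumptions, not trial data.

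**Inputs.**
- Trigger (period length other than 30), divisor x and the 50% compliance cut-off: SAP 5.4.1.
- Baseline diary completion of at least 80%: Protocol 6.1, criterion 6.
- Target of 30 days between treatment-phase visits, with an allowance of ±2: Protocol Schedule of Activities.
- Day count used for diary compliance: SAP 5.5.7.

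**Formulas.** Let m be the migraine headache days recorded on x entries.
- Prorated value: P = m × 30/x in every period.
- Literal value: L = m if the period counts as 30 days, otherwise m × 30/x.
- In a period counted as 30 days with m ≥ 1, the shortfall is (P − L)/P = 1 − x/30.

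**Size of the shortfall in one period.**

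| x | 1 − x/30 |
|---|---|
| 29 | 3.3% |
| 27 | 10.0% |
| 24 | 20.0% |
| 20 | 33.3% |
| 16 | 46.7% |

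With 30 expected entries, x = 16 is the lowest retained value: 15/30 = 50% is set to missing and 16/30 = 53.3% is kept. At baseline the 80% criterion requires 24 of 30 entries, which limits the shortfall to 20%.

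**Response status, baseline 10 with a complete diary.**
1. 5 days on 24 entries. Literal: 5, and (10 − 5)/10 = 50%, a responder. Prorated: 5 × 30/24 = 6.25, and (10 − 6.25)/10 = 37.5%, not a responder. The literal rule itself gives 6.25 if the period counts as 31 days.
2. 5 days on 29 entries. Literal: 5, and 50%. Prorated: 5 × 30/29 = 5.17, and (10 − 5.17)/10 = 48.3%. At the threshold, one missed entry changes the status.

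**The same gap at baseline works the other way.** Take 8 days on 24 entries in a baseline counted as 30 days, then 5 days in a complete month. Literal: (8 − 5)/8 = 37.5%. Prorated: baseline 8 × 30/24 = 10, and (10 − 5)/10 = 50%.

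**100% response.** With m = 0, 0 × 30/x = 0, so both readings agree.

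**Which periods count as 30 days.** SAP 5.4.1 does not say how length is counted. The allowed gaps between treatment-phase visits are 28, 29, 30, 31 and 32 days. By date difference, the 30-day gap is exempt. SAP 5.5.7 defines expected diary days in a way that "is calculated as date of injection at the end of the interval minus date of injection at the beginning of the interval +1", which turns the same gaps into 29, 30, 31, 32 and 33, so the 29-day gap would be exempt. That formula is written for compliance, and nothing says it governs the 30/x rule.

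**The case against.** The strongest reply is that the paragraph settles the matter itself. The sentence after the rule states its purpose and assumption, and harm would require a programmer to apply one clause and ignore the next. That stands, and it is why the point is minor. It does not make the operative clause correct.

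A second reply is that the period may mean days of diary data, since 5.4.1 describes the baseline in terms of daily data. Trigger and divisor would then coincide. This is strained, because the same sentence counts the non-missing days within the period, so the period must be something that can also contain missing ones.

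Some stronger readings are tempting but unsupported:

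- *Missing days will go unadjusted in the analysis.* The documents point the other way. The equal-rate sentence, the cross-reference in 5.5.1.2 and the compliant-days offset all fit proration.
- *Sections 5.5.1.2 and 5.5.10.2 set conflicting rules.* The first only refers back to 5.4.1, and the second is a separate model on raw counts. They are evidence of intent. The contradiction lies within 5.4.1.
- *One exempt gap in five means 20% of periods.* It is a count of permitted gaps, not a frequency. It also covers only treatment-phase gaps. The baseline has a 30- to 40-day eligibility period and no injection at its start, and patients who do not enter the open-label phase have no injection at Visit 6.
- *The literal rule favours galcanezumab.* A post-baseline shortfall exaggerates improvement only relative to the prorated value and only if a migraine day was recorded. A baseline shortfall does the reverse, and the same rule applies to both blinded arms.

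**Conclusion.** The clause is wrong as written, and the intention is clear. Taken literally, it leaves a period counted as 30 days with missing entries unadjusted, against the SAP's own stated assumption. The shortfall relative to the prorated value is 1 − x/30 when at least one migraine day was recorded, and a single missed entry can change response status at the threshold.

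These are per-period figures with assumed counts. The documents give neither the share of periods counted as 30 days nor the rate of missing entries, so the size and direction of any effect on the treatment difference cannot be computed. The stated power does not use this clause, and 100% response is the same either way. Severity: minor.

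**What to change.** In SAP 5.4.1, delete the period-length condition. Suggested wording: *In every retained period the count is multiplied by 30/x, where x is how many diary days in that period have an entry.* No exception is needed, because 30/x = 1 when x = 30.

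Apply this to the primary measure and to the other normalized monthly diary measures. Keep the separate rules for migraine attacks (carried-forward diary days, SAP 5.5.1.2) and for weekly counts (their own offset, SAP 5.5.10.3).

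Values stay the same in every period not counted as 30 days, and the trigger no longer depends on how length is counted. Which boundary days belong to a period can still affect both the count and x, and this edit does not settle that.

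The cost is one clause in the SAP. It needs no new data and no protocol change, and it does not affect the sample size.

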To compare galcanezumab with placebo with respect to 75% response rate	The percentage of patients with ≥75% reduction from baseline in monthly migraine headache days during the 3-month double-blind treatment phase	
To compare galcanezumab with placebo with respect to 100% response rate	The percentage of patients with 100% reduction from baseline in monthly migraine headache days during the 3-month double-blind treatment phase	

(Table CGAW.4.1. continued)

Objectives	Endpoints
Secondary Objectives Note: All other secondary objectives will be tested	
in both the total population (episodic and chronic migraine) and the episodic migraine subpopulation unless otherwise specified.	
To compare galcanezumab with placebo with respect to onset of effect	The initial month at which statistical separation in mean change from baseline in the number of monthly migraine headache days is demonstrated and maintained at all subsequent months through Month 3 in the double-blind treatment phase
	If the initial month of onset is Month 1, then the initial week at which statistical separation in mean change from baseline in the number of weekly migraine headache days is demonstrated and maintained at all subsequent weeks during Month 1
To compare galcanezumab with placebo with respect to change in use of acute headache treatment	The overall mean change from baseline in the number of monthly days with acute headache medication use during the 3-month double-blind treatment phase
To compare galcanezumab with placebo with respect to change in monthly headache days	The overall mean change from baseline in the number of monthly headache days during the 3-month double-blind treatment phase
To compare galcanezumab with placebo with respect to change in International Classification of Headache Disorders (ICHD) migraine headache days	The overall mean change from baseline in the number of monthly International Classification of Headache Disorders (ICHD) migraine headache days during the 3-month double-blind treatment phase
To compare galcanezumab with placebo with respect to change in monthly migraine headache hours	The overall mean change from baseline in the number of monthly migraine headache hours during the 3-month double-blind treatment phase
To compare galcanezumab with placebo with respect to change in monthly headache hours	The overall mean change from baseline in the number of monthly headache hours during the 3-month double-blind treatment phase

(Table CGAW.4.1. continued)

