For models where the unstructured covariance matrix is not utilized, the sandwich estimator (Diggle et al. 1994) will be used to estimate the standard errors of the fixed effects parameters. The sandwich estimator is utilized by the EMPIRICAL option in SAS. When the sandwich estimator is utilized, the Kenward-Roger approximation for denominator degrees of freedom cannot be used. Instead, the denominator degrees of freedom will be partitioned into between-subject and within-subject portions by the DDFM=BETWITHIN option in SAS.

For the binary secondary efficacy measures where the objective is to assess proportion of patients with X% response during the 3-month double-blind treatment phase, the endpoint for galcanezumab compared with placebo will be estimated as the treatment main effect from the categorical MMRM analysis assessing the average response rate across Month 1, Month 2, and Month 3.

The number of weekly migraine headache days in Month 1

If statistically significant improvement is observed at Month 1 and maintained for all the subsequent months during the double-blind treatment phase for the number of monthly migraine headache days, the number of weekly migraine headache days in Month 1 will be analyzed to identify the earliest week where the statistically significant improvement is observed and maintained for all the subsequent weeks in Month 1 for patients who have a monthly diary compliance rate greater than 50% for Month 1.

The number of weekly migraine headache days in Month 1 can be considered as ordinal data with possible values of 0, 1, 2, 3, 4, etc. and will be analyzed using an ordinal repeated measures model using the GLIMMIX procedure in SAS. In this model, a proportional odds model with cumulative logit link will be used, and a random intercept will be applied to the observations for each patient to account for repeated measures. The model will include the fixed, categorical effects of treatment, pooled country, week, and treatment-by-week interaction, as well as the continuous, fixed covariate of weekly baseline number of migraine headache days and weekly baseline number of migraine headache days-by-week interaction. Log (number of compliant calendar days within each week/7) will be included as the offset in the model. For weekly diary

compliance rate ≤50%, the number of weekly migraine headache days during that week will be considered missing.

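### The weekly onset model admits only patients with Month 1 diary compliance above 50%, so usable early weeks are discarded because of later behaviour; the effect is probably small

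*SAP*

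**What the plan says.** Weekly onset is the second half of a secondary objective in SAP Table CGAW.4.1: if onset is in Month 1, the trial seeks "the initial week at which statistical separation in mean change from baseline in the number of weekly migraine headache days is demonstrated" and then maintained through the month. It is assessed in the total and episodic populations.

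Four rules decide whose weekly data count:

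- **Monthly rule, SAP 5.4.1.** When a month's compliance is 50% or less, "then all endpoints to be derived from the ePRO diary data for that 1-month period will be considered missing".
- **Entry condition, SAP 5.5.10.3.** The weekly model is run "for patients who have a monthly diary compliance rate greater than 50% for Month 1".
- **Weekly rule, SAP 5.5.10.3.** For a weekly "compliance rate ≤50%, the number of weekly migraine headache days during that week will be considered missing". The model also has an offset, the log of compliant days divided by 7.
- **Denominator, SAP 5.5.7.** For someone who leaves early, the "compliance rate for the last month of that patient will be calculated with a denominator of 30 days", or the actual interval if longer. For someone who stays, it is the number of days between injections plus 1.

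SAP 5.4.1 defines Week 1 as days 1-7, Week 2 as days 8-14, Week 3 as days 15-21 and Week 4 as the remainder.

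**The concern.** The monthly rule has a clear purpose for a monthly count: it stops a 30-day figure being scaled up from few diary days. Weekly counts are not scaled to 30 days, and incomplete weeks are already handled by the weekly rule and the offset. Any week removed by the monthly condition alone has therefore passed the SAP's own test for a usable week.

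The condition also looks forward in time. Whether a randomised patient's Week 1 count is used depends on whether that patient stays and keeps the diary in Weeks 2 to 4. This is selection on post-randomisation behaviour. It sits badly with SAP 5.5.1.2, which describes repeated-measures analyses as using all observed data. If a patient stops because of a bad first week, that week is the information a repeated-measures model needs to account for the stopping.

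Onset is dated by the first significant week that is maintained, so a small change in Week 1 could move the reported week when the result is near the threshold. The sensitivity analyses in SAP 5.5.10.2 concern the primary outcome only and would not show this.

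**Working it through.** **The plan's own figures.** The documents give no figure for the weekly analysis. The input used here is the 10% discontinuation in Protocol 10.1 and SAP 5.2, so I checked that it reproduces the stated power, using power = Φ(d × √(n/2) − 1.96) with n = 0.9 × N/2 per arm.

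- Total: n = 0.9 × 210 = 189, d = 0.39. Φ(3.79 − 1.96) = 96.6%, against a stated 96%.
- Episodic: n = 0.9 × 125 = 112.5, d = 0.46. Φ(3.45 − 1.96) = 93.2%, against a stated 93%.

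**Which weeks are lost.** Take a patient who leaves, with a complete diary up to the last diary day and a denominator of 30. A week is usable when more than 50% complete, that is at least 4 of 7 days.

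| Last diary day | Month 1 compliance | Weeks used under the plan | Weeks passing the weekly rule alone |
|---|---|---|---|
| 4-6 | 13.3%-20.0% | 0 | 1 (partial Week 1) |
| 7-10 | 23.3%-33.3% | 0 | 1 (full Week 1) |
| 11-13 | 36.7%-43.3% | 0 | 2 (full Week 1; 4 to 6 days of Week 2) |
| 14-15 | 46.7%-50.0% | 0 | 2 (both full) |
| 16 | 53.3% | 2 | 2 |

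One more diary day, from 15/30 to 16/30, restores both weeks.

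**Patients who stay but stop the diary.** A visit interval of 30 ± 2 days (Protocol Section 2) gives a denominator of 29 to 33. Fourteen complete days is then 14/29 = 48.3% down to 14/33 = 42.4%, excluded in every case. Gaps can do the same: 7, 4 and 4 diary days in Weeks 1 to 3 and none after gives 15/30 = 50%, so three usable weeks are dropped.

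**How many leavers.** Assume a constant hazard with 10% leaving over 90 days, so the proportion gone by day t is 1 − 0.9^(t/90).

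- By day 15: 1 − 0.9^(15/90) = 1.74%; × 420 = 7.3 patients.
- Last day 7-15 (a full Week 1 lost): 0.9^(6/90) − 0.9^(15/90) = 0.9930 − 0.9826 = 1.04%; × 420 = 4.4.
- Last day 14-15 (both weeks complete): 0.9^(13/90) − 0.9^(15/90) = 0.9849 − 0.9826 = 0.23%; × 420 = 1.0.

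As an extreme, suppose all 42 leavers go in Month 1, spread evenly over 30 days. The counts become 42 × 15/30 = 21 (5%), 42 × 9/30 = 12.6 and 42 × 2/30 = 2.8. Diary stoppers who remain would add to either set; the documents give no rate.

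**What it could do to the Week 1 difference.** If a fraction f of one arm is excluded and their mean weekly count differs from the rest of that arm by D days, that arm's mean shifts by f × D. Assuming D = 1 and exclusion in one arm only, f = 2% gives 0.02 days and f = 5% gives 0.05 days. With equal f and equal D in both arms the shift in the difference is 0.

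**The case against.** **Scope of 5.4.1.** The monthly rule stands under the primary measure and speaks of a monthly interval. The paragraph after it extends the approach to measures normalised to 30 days, which weekly counts are not. This stands: 5.4.1 alone does not settle the matter. The weekly restriction rests on 5.5.10.3, whose wording is explicit.

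**Same patients.** The weekly analysis follows only if Month 1 separates, so one could want onset dated in patients with an observed Month 1 value. The SAP does not give this reason. The monthly analysis does not use that set either: Table CGAW.5.4 admits anyone with a baseline and at least one postbaseline observation. A patient with a poor Month 1 and good later diaries stays in the monthly model and is shut out of the weekly one.

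**Size and standing.** The filter is prespecified. It affects a conditional secondary endpoint outside the gatekeeping sequence, with no multiplicity adjustment (Protocol 10.3.3.3). Inclusion criterion 6 requires at least 80% diary completion at baseline, which makes heavy diary-stopping soon after randomisation less likely. All of this stands and keeps the point minor.

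**Stronger readings.** A reader might infer that everyone who stops by mid-month loses two complete weeks. Only a last diary day of about 14 or 15 does that; stopping before day 7 loses no full week. A reader might also infer that the Week 1 effect is materially diluted and onset dated too late. Suppose Week 1 rates of 0.40 and 0.335 migraine days per day, a difference of 7 × 0.065 = 0.455 days. Diluting this by 19% (0.086 days) through a 5% exclusion on placebo needs those patients to average 0.086/0.05 = 1.7 days more than the rest of their arm, with no similar dependence on galcanezumab. None of these figures is in the documents. Leaving for adverse events on galcanezumab would be a different selection.

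**Conclusion.** The monthly entry condition in SAP 5.5.10.3 deletes weeks that the SAP itself counts as usable and makes early-week outcomes depend on later behaviour. It adds no data-quality protection beyond the weekly rule and offset. That follows from the text and needs no assumption.

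The size does rest on assumptions. With a constant hazard at 10% discontinuation, about 7 of 420 patients are affected through leaving, about 4 of them losing a full Week 1 and about 1 losing both full weeks; diary stoppers who stay are uncounted. A shift of 0.02 to 0.05 days in the Week 1 difference needs one-sided exclusion of 2% to 5% and an assumed gap of 1 day; balanced exclusion with equal gaps gives none. The documents do not show whether early stopping differs by arm or relates to outcome, so no direction of bias can be claimed. The primary and key secondary results and the planned power are unaffected. Severity is minor: an optional improvement.

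**What to change.** In SAP 5.5.10.3, delete the words "for patients who have a monthly diary compliance rate greater than 50% for Month 1". Keep the weekly 50% rule and the offset, so that every ITT patient with a baseline and at least one compliant week in Month 1 enters the weekly model. In SAP 5.4.1, state that the monthly 50% rule applies to whole-month endpoints only. The restricted set can optionally be kept as a sensitivity analysis.

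The cost is one clause removed and one sentence clarified, with no new data. The weekly analysis set becomes slightly larger than the set with an observed Month 1 value, which the report should say.
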